2.0 OBJECTIVES

2.1 Primary Objectives

1. To assess the safety, tolerability, and efficacy of sofosbuvir based DAA therapy for 12 – 24 weeks in HIV/HCV coinfecting participants pre- and post-liver transplant.
2. To assess the safety, tolerability, and efficacy of a fixed dose combination (FDC) of sofosbuvir and ledipasvir (SOF/LDV) for 12 to 24 weeks in HIV/HCV coinfecting participants pre or post liver transplant.

2.2 Secondary Objectives

1. To evaluate changes in HCV viral kinetics with SOF/LDV or sofosbuvir based DAA therapies in HIV/HCV coinfecte subjects with pre or post liver transplant HCV
2. To evaluate the proportion of subjects with HCV viral loads below the level of quantification at various time points of the study
3. To determine sustained virologic response rates with FDC SOF/LDV or sofosbuvir based DAA therapies.
4. To identify the determinants of response to interferon sparing therapy in eradicating HCV in pre or post liver transplant HIV/HCV coinfecte subjects
5. To identify the host genetic, protein, gene, and proteomic factors that are associated with responses to interferon (IFN) sparing therapy in pre or post liver transplant HIV/HCV coinfecte subjects (*prospective arm only*)
6. To determine if levels of interferon-stimulated genes (ISG) expression in PBMCs or liver can predict rapid virologic response (RVR), end of treatment response (ETR), and sustained virologic response (SVR) in participants receiving IFN sparing therapy (*prospective arm only*)
7. To evaluate the proportion of subjects whose ALT normalizes during therapy and between baseline and SVR
8. To evaluate the emergence of viral resistance during therapy with FDC SOF/LDV or sofosbuvir based DAA therapies
9. To evaluate change in liver fibrosis and liver function before and after treatment with FDC SOF/LDV or sofosbuvir based DAA therapies.

3.0 STUDY DESCRIPTION

Approximately fifty HIV/HCV coinfecte patients with decompensated liver disease will be enrolled in the study. Ten (up to twenty) subjects will be treated with FDC SOF/LDV pre or post liver transplant and followed prospectively. Forty + subjects will be enrolled retrospectively with the intent to capture all patients who have been exposed to sofosbuvir based DAA therapies at participating sites since 1/2014, and to mirror the population being enrolled prospectively.

In addition, participants in the retrospective arm will be contacted to consent to one prospective study visit for liver staging to determine rates of reversal of decompensation, reversal of cirrhosis and improvements in graft survival post treatment, and for future contact by the NIH Clinical Center to assess longer term outcomes when this study ends.

3.1 Retrospective Arm

Participating sites will collect clinical data on all of the HIV/HCV co-infected patients with decompensated liver disease (CPT >7 pre or post liver transplant) treated with sofosbuvir based DAA therapies since 1/2014 at their center. This will be done under IRB approved waiver of consent if possible so that all treated patients meeting the inclusion criteria can be included to avoid statistical bias. Data collected will mirror the data collected in the prospective arm. In addition, participants will be contacted to provide consent to return to the site for one visit for current liver staging to evaluate reversal of fibrosis (unless liver staging by Fibroscan or liver biopsy was done in the previous 12 months), and to be contacted in the future by the NIH Clinical Center for long term follow-up.

- Efficacy will be defined as HCV RNA undetectable \geq 12 weeks post end of sofosbuvir based DAA therapy.
- Safety and tolerability will be defined by
 - discontinuation rates
 - rates of hospitalization during DAA therapy
 - frequency of anemia requiring blood transfusion or EPO
 - survival.
- Reversal of decompensation: defined by CP score and MELD score at last follow-up (evaluated at time to event given the variability in length of follow-up post treatment)
- Reversal of fibrosis: defined by liver fibrosis by Fibroscan or biopsy at last follow-up (evaluated at time to event given the variability in length of follow-up post treatment)

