3.3 STUDY ENDPOINTS

3.3.1 Primary Endpoints

- Safety and tolerability of SOF/LDV for 12 to 24 weeks
- Proportion of subjects achieving SVR₁₂ (HCV RNA < LLOQ 12 weeks after completion of treatment)

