4.1.1 Primary Endpoint

The primary efficacy endpoint is SVR₁₂ (HCV RNA < LLOQ 12 weeks after cessation of therapy).

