4.3 Data Handling Conventions

Missing data can have an impact upon the interpretation of the trial data. Other than the endpoints discussed below, values for missing data will not be imputed.

For the analysis of post-baseline categorical efficacy endpoints, if a data point is missing and is preceded and followed in time by values that are deemed successes, then the missing data point will be termed a success; otherwise the data point will be termed a failure.

Any subject with missing data due to premature discontinuation of the study medication will be considered a failure at the time points on, or following, the date of discontinuation. If no HCV RNA values are obtained after the last dose of study medication, the subject will be considered a treatment failure for the SVR endpoints.

Where appropriate, safety data for subjects that did not complete the study will be included in summary statistics. For example,

- If a subject received study medication, the subject will be included in a summary of adverse events according to the treatment received; otherwise, if the subject is not dosed then they will be excluded from the summary.
- If safety laboratory results for a subject are missing for any reason at a time point, the subject will be excluded from the calculation of summary statistics for that time point. If the subject is missing a pre-dose value, then the subject will be excluded from the calculation of summary statistics for the pre-dose value and the change from pre-dose values.

Values for missing vital signs data will not be imputed; however, a missing Day 0 result will be replaced with a screening result, if available.

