4.4 Efficacy Analyses

4.4.1 Primary Analysis

The primary efficacy endpoint is SVR₁₂ (HCV RNA <LLOQ 12 weeks after cessation of therapy.)

There is no active comparator group for this study (as in most clinical trials with all oral therapies in these populations).

In the primary efficacy analysis, an exact Clopper-Pearson 95% confidence interval will be computed for the SVR₁₂ rate.

The primary analysis will be performed after all enrolled subjects have been followed through 12 weeks post-treatment or discontinued from study.

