8.9.1 Treatment Failure Criteria After Stopping SOF/LDV

- Have detectable HCV RNA during the post-treatment period (after having achieved HCV RNA <LLOQ at end of treatment).

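### The primary efficacy outcome is defined by two thresholds and two time windows, and the post-treatment failure rule in 8.9.1 conflicts with SVR12 in 4.4.1

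*Combined protocol and SAP*

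**What the plan says.** Three sections of the combined protocol and SAP give the primary efficacy endpoint in the same terms: 3.3.1 ("HCV RNA < LLOQ 12 weeks after completion of treatment"), 4.1.1 ("HCV RNA < LLOQ 12 weeks after cessation of therapy") and 4.4.1 ("HCV RNA <LLOQ 12 weeks after cessation of therapy"). The threshold is the LLOQ and the time is 12 weeks. Section 7.9 allows 14 days either side for prospective follow-up visits.

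Section 3.1 has its own rule for the retrospective arm: "Efficacy will be defined as HCV RNA undetectable", at or after "12 weeks post end of sofosbuvir based DAA therapy". It sets no upper time limit. Section 6.3 has retrospective data recorded at 3 months and again at 6 months or more after treatment, without windows.

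Section 8.9.1, which belongs to the prospective-arm chapter, lists as treatment failure those who "Have detectable HCV RNA during the post-treatment period", provided they were below the LLOQ at end of treatment.

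Section 4.3 counts a missing categorical efficacy value as a success only if it is "preceded and followed in time by values that are deemed successes", and otherwise as a failure.

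The abbreviation list gives LOD and LLOQ as separate terms. The on-treatment failure rules in 8.9 refer to the LLOQ. Section 4.4.1 plans one exact 95% interval for the SVR12 rate, and 4.1 bases its precision on 50 patients.

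**The concern.** Undetectable is a stricter requirement than below the LLOQ. An assay can find HCV RNA in a sample at a level too low to quantify, and the two rules classify that result in opposite ways. The retrospective arm is most of the study, so the rule in 3.1 is not a side issue.

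Two things are at stake. The first is what the SVR12 rate means: if the arms are analysed together, some patients would be scored by a strict threshold at any time from 12 weeks on, and others by a looser threshold at a fixed visit. A difference between the arms could then come from the definitions alone. The second is the internal consistency of the report. Relapse is a secondary endpoint (3.3.2, 4.1.2) and virologic failure is to be summarised (4.4.2). If failure is taken from 8.9.1, one prospective patient could appear both among the SVR12 successes and among the failures.

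**Working it through.** **Step 1. The plan's own figures.** Inputs: n = 50 and Table 1 (section 4.1); exact Clopper-Pearson 95% interval (section 4.4.1). For x successes, the lower limit is the 0.025 quantile of Beta(x, n − x + 1), and the upper limit is the 0.975 quantile of Beta(x + 1, n − x), or 1 when x = n.

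| x of 50 | Table 1 | Recomputed |
|---|---|---|
| 50 | 0.929–1 | 0.9289–1 |
| 48 | 0.863–0.995 | 0.8629–0.9951 |
| 46 | 0.808–0.978 | 0.8077–0.9778 |
| 44 | 0.757–0.955 | 0.7569–0.9547 |
| 42 | 0.709–0.928 | 0.7089–0.9283 |
| 40 | 0.663–0.900 | 0.6628–0.8997 |

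Table 1 is right for n = 50. Its footnote refers to 25, which is a separate slip: 25/25 would give 0.863–1.

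**Step 2. How one result is classified.** Take a post-treatment week 12 result that is detected but below the LLOQ.

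| Patient | Under 4.4.1 (also 3.3.1, 4.1.1) | Under the arm's own rule |
|---|---|---|
| Retrospective | SVR12 | Not efficacy (3.1) |
| Prospective, below LLOQ at end of treatment | SVR12 | Treatment failure (8.9.1) |

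The definitions agree on threshold for any result that is undetectable, and for any result at or above the LLOQ. They part only in the band between.

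**Step 3. Timing.** A prospective value belongs to week 12, give or take 14 days. A retrospective value taken at 6 months or later satisfies 3.1 with no reference to week 12. If the 3-month value is missing, 4.3 makes the patient a success when earlier and later values are successes, and then 3.1 and 4.3 agree. They disagree only when a late undetectable value has no earlier success on record.

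**Step 4. Share of the sample.** Section 3.0 plans 40 or more retrospective patients and 10, up to 20, prospective. The retrospective share is 40/50 = 80% or 40/60 = 67%.

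**Step 5. Size per patient.** At n = 50 one reclassified patient moves the rate by 1/50 = 2 percentage points. The documents do not say how many results will fall in the band, so the range 0 to 3 below is an assumption.

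| Reclassified | From 50/50 | From 48/50 |
|---|---|---|
| 0 | 100% (0.9289–1) | 96% (0.8629–0.9951) |
| 1 | 98% (0.8935–0.9995) | 94% (0.8345–0.9875) |
| 2 | 96% (0.8629–0.9951) | 92% (0.8077–0.9778) |
| 3 | 94% (0.8345–0.9875) | 90% (0.7819–0.9667) |

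If the prospective arm is analysed alone, one patient counts for more. The lower limit falls from 0.692 (10/10) to 0.555 (9/10), or from 0.832 (20/20) to 0.751 (19/20).

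**The case against.** The endpoint is stated consistently in the sections that govern the analysis, and 3.1 is a descriptive section that speaks of efficacy without naming SVR12. It may be loose wording. Section 4.4.2 also leaves efficacy details to a statistical analysis plan. This is fair as an account of how the mismatch arose, but nothing in the supplied text resolves it.

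Several stronger readings are tempting, and the documents do not support them.

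- A reader might infer that one patient's result can carry all three labels. It cannot: 3.1 applies only to the retrospective arm and section 8 only to the prospective arm. The overlap of success and failure exists only among the 10 to 20 prospective patients, and only for those below the LLOQ at end of treatment.
- A reader might take pooling of the arms as stated. Section 4.1 uses the word combined for pre- and post-transplant patients, and 4.2.1 speaks of those given study drug, which could mean the prospective arm alone. Pooling is the likelier reading because 50 is the sum of both arms (3.0) and one interval is planned. On the other reading Table 1 would not describe the analysis, and the 8.9.1 conflict would remain.
- A reader might infer that a cured retrospective patient with only a late negative value is generally failed by 4.3. That is not so for a patient with an earlier value below the LLOQ.
- The separate listing of LOD and LLOQ supports treating them as different limits, but it is not decisive. The eligibility criterion that uses level of detection (5.2) concerns HIV, and no HCV assay limits are given.

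**Conclusion.** The inconsistency is real and concerns the primary efficacy outcome. In the retrospective arm it lies between 3.1 and the SVR12 definition in 4.4.1, in both threshold and time window. In the prospective arm it lies between 8.9.1 and 4.4.1, in threshold.

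The effect is 2 percentage points per reclassified patient at n = 50. The total is unknown: it depends on how many results are detected but below the LLOQ, and the threshold part is nil if there are none or if an assay's two limits coincide. The consequence for a single mixed interval rests on the inference that the arms are pooled; the conflicting definitions themselves do not. The finding does not show that the SVR12 estimate will be materially biased. It shows that the plan as written does not fix how these results are scored, and that this should be settled before outcomes are classified.

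**What to change.** For the efficacy analysis:

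- Score both arms by the 4.4.1 definition, HCV RNA below the LLOQ whether detected or not, at the post-treatment week 12 or 3-month time point. Amend 3.1 to match.
- State one window for both arms, for example the 14 days either side already in 7.9.
- Use a later value only when the week 12 value is missing, no intervening value is at or above the LLOQ, and no HCV retreatment has been given. Align the missing-data rule in 4.3 with this.
- Report undetectable HCV RNA as a supportive result only.
- State whether the primary interval pools the two arms.

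Sections 8.9.1 and 4.4.1 must be reconciled so that one result cannot be reported both as SVR12 and as failure or relapse. The 8.9.1 threshold is for the sponsor to decide, since virologic failure and relapse also lead to return visits and resistance testing (7.10, 12).

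The cost is wording in the protocol and SAP. Retrospective HCV RNA is already abstracted (6.3, 11.2), and no added visits or samples are needed.

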3.2 Prospective Arm

The cohort of pre-transplant patients with cirrhosis due to hepatitis C will be treated with SOF/LDV until LT or for a maximum of 24 weeks. Patients with and without HCC within Milan criteria are eligible. Another cohort of liver transplant recipients with recurrent HCV infection post liver transplant will also be treated with SOF/LDV for a period of 12 weeks (no cirrhosis) or 24 weeks (cirrhosis). Patients with fibrosing cholestatic hepatitis are eligible and will be treated for 12 weeks.

Starting with Day 0, all subjects will receive SOF/LDV for 12 or up to 24 weeks. The total amount of time required to complete all the study visits is approximately 56 - 68 weeks from the screening period through the end of the follow-up visits:

- Up to 8 weeks Screening period
- 12 or 24 week treatment period
- 12 and 24 week post-treatment follow-up visits (SVR12 and SVR24)
- 36 weeks post-treatment to assess late viral relapse

Subjects identified to have mutations leading to SOF or LDV resistance following sequencing and phenotypic analysis will be requested to return at 12-week intervals for up to 36 weeks to determine the time required for the resistant virus to return to background levels.

3.3 STUDY ENDPOINTS

3.3.1 Primary Endpoints

- Safety and tolerability of SOF/LDV for 12 to 24 weeks
- Proportion of subjects achieving SVR₁₂ (HCV RNA < LLOQ 12 weeks after completion of treatment)

3.3.2 Secondary Endpoints

- Correlation of the slope of HCV viral load decline (early viral kinetics) with sustained virologic response at 24 weeks post-treatment (SVR₂₄)
- Proportion of subjects achieving SVR₄ and SVR₂₄ (HCV RNA < LLOQ at 4 and 24 weeks after completion of treatment)
- RVR₄, (RVR₄: HCV RNA < LLOQ at Week 4): Correlation of early viral kinetics with the percentage of subjects achieving RVR₄.
- End of treatment response (ETR: HCV RNA < LLOQ at end of treatment). Correlation of early viral kinetics to the percentage of subjects who achieve ETR.
- Correlation of early viral kinetics to the percentage of subjects who achieve SVR₁₂.
- Viral relapse: Correlation of early viral kinetics with the percentage of subjects who develop viral relapse.
- Differential interferon sensitive gene (ISR) response to therapy in subjects treated for 12 weeks who do and do not attain RVR₄ and SVR.
- Host genetic and proteomic factors in subjects with differential RVR₄ and SVR HCV quasispecies evaluation at baseline and during therapy to determine emergence of resistance subjects who attain RVR₄, and those who achieve SVR.
- HIV and HCV immunologic (adaptive and innate) correlates of SVR and RVR
- Change in liver fibrosis before and after treatment as determined by standard of care liver staging method.

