6.3 Time-points

Clinical data from day 0 (start of treatment), week 4, and end of treatment (week 12 or 24 depending on treatment duration) will be recorded in the Redcap database. Data will also be recorded at 3 months post treatment with DAA and again at 6 or more months post treatment with DAA. A complete list of study procedures to be captured is outlined in the Schedule of Events (Section 11)

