7.6 Study Visits during treatment

All participants will be seen on days 0, weeks 4, and week 12 EOT, (or week 24 if treated for 24 wks).

- Weeks 4 (+/- 7 days)
- Week 12 [and 16, 20, 24 if applicable] (+/- 10 days)

Plasma HCV RNA will be obtained on each visit. Subjects who fail to achieve >2 log₁₀ HCV RNA drop at this time (unless >2 log drop would be below LLOQ) will be discontinued from therapy unless a review by the PI/Operations Committee determines otherwise.

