11 SCHEDULE OF EVENTS

11.1 Schedule of Events Prospective Arm

	Screening	Day 0	Week 4	Week 12*	Week 24*	Day of Transplant	3M post treatment	6 M post treatment
			Month 1	Month 3	Month 6 if treated for 24 weeks	If transplant occurs post treatment with study drug	3 Months post treatment	6 Months or greater post treatment
History and Physical	X	X	X	X	X			X
Vital signs and Weight		X	X	X	X		X	X
Height	X							
Urinalysis		X						
Pregnancy Test: Urine		X ¹						
HBsAg	X							
Anti-HBc	X							
Virology Panel: (Historical only)								
Anti-HIV Ab	X							
Anti-HCV Ab	X							
HCV Genotype	X							
Plasma HCV RNA Levels		X	X	X	X		X	X
CD4+ T-cell count		X ²		X ²	X ²		X ²	X ²
HIV-1 RNA (bDNA or PCR)		X ²		X ²	X ²		X ²	X ²
Standard of care liver staging	X			X ³	X			
SERUM CHEMISTRY								
Alanine aminotransferase (ALT)		X	X	X	X		X	X
Albumin		X		X	X			X
Alkaline phosphatase		X	X	X	X		X	X
Aspartate aminotransferase (AST)		X	X	X	X		X	X
Bicarbonate (If on ARV regimen containing tenofovir)		X	X	X	X		X	X
Bilirubin, total, direct		X	X	X	X		X	X
Glucose (repeat during treatment, but only if abnormal at baseline)		X	X	X	X			
Phosphate (If on ARV regimen containing tenofovir)		X	X	X	X		X	X
Potassium (If on ARV regimen containing tenofovir)		X	X	X	X		X	X
Sodium		X	X	X	X		X	X
Serum Creatinine		X	X	X	X		X	X
HEMATOLOGY								
Hemoglobin		X		X	X			
Platelet Count		X		X	X			
White Blood Cell (WBC) Count		X		X	X			
Differential		X		X	X			
Neutrophils		X		X	X			
Lymphocytes		X		X	X			
INR		X		X	X			
RESEARCH								

Limited HCV Viral Kinetics		X	X	X	X			
Liver explant tissue (if achieved SVR)						X ⁴		
HLA	X ²							
Blood draw for immunologic studies		X	X	X	X		X	X
Paxgene DNA (6.5 ml)		X						
Paxgene RNA (2.5 ml)		X	X	X	X		X	
IL28B rs12979860 (run off Paxgene DNA sample)		X						
Blood for storage (8 cc SST serum, 6 cc EDTA)		X	X	X	X		X	X

*Subjects who are terminated early or who have early treatment discontinuation should have an end of treatment visit as soon as possible after therapy is stopped.

¹ Urine pregnancy test for females with childbearing potential must be negative on Day 0 prior to dosing with study agent

² documented historic results are acceptable. If not available, not required unless considered standard of care, or may be run on stored samples. For HIV-1 RNA and CD4+ T-cell counts, test results from primary care provider should be obtained per standard of care (every 3 months)

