12 MECHANISTIC STUDIES: PROSPECTIVE ARM

Viral Kinetics

Samples from Days 0, week 4, and end of treatment (EOT) will be used to assess HCV viral load levels.

HCV Virologic Studies

Full length HCV genome pyro sequencing may be performed using the protocol as described and compared for variability of sequences [45].

rs12979860 (IL28B) Genetic Variant

IL28B genetic variants have been shown to predict HCV treatment induced clearance. The IL28B assay is a real-time PCR assay that utilizes 5-prime nuclease activity of a thermostable polymerase and unique primers and SNP-specific probes to determine the genotype. Test results will not be used as inclusion or exclusion criteria, or to randomize subjects into treatment groups.

Immune Responses to HCV and HIV

Both humoral and cellular immunity against HCV and HIV will be estimated before and during treatment to assess the effect of HCV treatment on host immune response against HCV. We may also perform multiplex PCR assays to detect ISGs before and during treatment.

HCV Genotypic and Phenotypic Resistance Monitoring

Serum samples for genotypic and phenotypic monitoring will be collected

Resistance monitoring will be completed in all subjects who received study drug and were virologic failures as defined.

Subjects who are determined by sequencing and phenotypic analysis to have had mutations leading to SOF resistance will be requested to return at 12 week intervals for up to 48 weeks after the last dose of study drug to determine the time for the resistant virus to return to background levels.

RNA Extraction from liver tissue

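### The early viral-load slope uses the same Week 4 sample that defines RVR4, so their correlation is not prediction; for the later outcomes the slope is left-censored, with no stated rule for values below LLOQ

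*Combined protocol and SAP*

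**What the plan says.** Section 3.3.2 names the predictor and its first use: "Correlation of the slope of HCV viral load decline (early viral kinetics) with sustained virologic response" at 24 weeks after treatment. It then lists the same kinetics against four further outcomes: RVR4, ETR, SVR12 and relapse. The RVR4 item reads "Correlation of early viral kinetics with the percentage of subjects achieving" RVR4, and RVR4 is defined there as HCV RNA below LLOQ at Week 4.

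The sampling is fixed elsewhere:

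- Section 12, Viral Kinetics: "Samples from Days 0, week 4, and end of treatment (EOT) will be used to assess HCV viral load levels".
- Section 7.6: "All participants will be seen on days 0, weeks 4, and week 12 EOT, (or week 24 if treated for 24 wks", with "Plasma HCV RNA will be obtained on each visit". The visit windows there also mention Weeks 16 and 20, both after Week 12.
- Section 11.1: the row "Limited HCV Viral Kinetics" is marked at Day 0 and Weeks 4, 12 and 24.
- Section 6.3, retrospective arm: "Clinical data from day 0 (start of treatment), week 4, and end of treatment".

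No section gives a window or formula for the slope, or says how a quantitative value below LLOQ is handled. Section 4.3 deals with missing data only. Section 4.4.2 leaves the detail of efficacy analyses to a statistical analysis plan, and the combined document contains no such rule.

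**The concern.** With one measurement before treatment and the next at Week 4, an early slope is in effect the difference between those two values. RVR4 is the second value cut at LLOQ. A correlation between the two describes how they were constructed, not whether fast early decline foretells response.

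The other four outcomes have a different problem. Once a subject is below LLOQ at Week 4, the size of the decline is unknown beyond a lower bound, and that bound is set by baseline load. Sections 1.0 and 1.1 describe quick suppression on this regimen in an earlier coinfected study, so many subjects may be in that position. An analyst must then choose a number to stand for values below LLOQ, and the plan leaves that choice open. At stake is the interpretation of five listed secondary items that serve secondary objective 1. The primary endpoint is not affected.

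**Working it through.** The plan states no effect size, power or sample size for these correlations, so there is no figure of its own to reproduce here.

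**Inputs from the documents.** HCV RNA at Day 0 and Week 4 with nothing between (Sections 7.6, 11.1 and 12); RVR4 means Week 4 HCV RNA below LLOQ (Section 3.3.2).

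**Inputs assumed.** The documents give neither the LLOQ nor any viral-load distribution. The simulation used 400,000 subjects per setting; baseline log10 load normal with mean 6 and SD 0.8, clipped to 3-7.8; true decline normal with mean 4.5 to 6.5 and SD 0.7, independent of baseline; LLOQ 15 or 25 IU/mL. RVR4 rates then run from about 38% to 96%.

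**Step 1, overlap.** Write V0 and V4 for the Day 0 and Week 4 values. The two-point slope per week is (log10 V0 - log10 V4)/4, and RVR4 is the indicator that V4 < LLOQ. V4 appears in both. This step needs no simulation.

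**Step 2, censoring.** For every RVR4 achiever the slope is known only to exceed (log10 V0 - log10 LLOQ)/4. With LLOQ 25, log10 LLOQ = 1.398:

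- baseline 5 log10: (5 - 1.398)/4 = 0.90 per week
- baseline 6 log10: (6 - 1.398)/4 = 1.15 per week
- baseline 7 log10: (7 - 1.398)/4 = 1.40 per week

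If one constant replaces all values below LLOQ and the divisor is fixed at 4 weeks, the slope among achievers is an exact linear function of baseline (correlation 1.00).

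**Step 3, dependence on the substituted value.** Slope-RVR4 correlation in the same simulated settings:

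| Value used for below LLOQ | Correlation, range over settings |
|---|---|
| LLOQ | -0.27 to 0.00 |
| LLOQ/2 | -0.15 to +0.24 |
| 1 IU/mL | +0.12 to +0.73 |
| uncensored true decline | +0.29 to +0.53 |

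The same subjects can give a negative, null or positive answer.

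**Step 4, slope against baseline over all subjects** (LLOQ substituted). The correlation is 0.50 to 0.60 at the lowest RVR4 rates (38-46%), 0.88 once 74% reach RVR4, and 0.99 at 94-96%.

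**Step 5, a different model.** Suppose the Week 4 value, rather than the decline, is independent of baseline (Week 4 SD 0.7, baseline SD 0.5-0.8, LLOQ 12-43, RVR4 50-90%). The slope-RVR4 correlation is then 0.12 to 0.44 with LLOQ substituted and 0.22 to 0.60 with LLOQ/2. Adding a Week 12 value below LLOQ and fitting three points by least squares (times 0, 4, 12) gives a decline of 0.0714·log10 V0 + 0.0179·log10 V4 - 0.0893·log10 LLOQ. Week 4 is still in it, now with the opposite sign, and the correlation becomes -0.03 to -0.14. Using the end-of-treatment sample therefore does not remove the overlap.

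**The case against.** The strongest reply is that this is an under-specified descriptive item with little riding on it. Section 4.1.2 omits kinetics from the secondary efficacy endpoints, Section 4.1.4 lists viral kinetic parameters among evaluations that may be done, and Section 11.1 calls the sampling limited. No test, error rate or decision depends on it, and a later analysis plan could define the window and the handling of low values. That fairly limits the stakes. It does not rescue the RVR4 item, because no definition of an early slope on this schedule can exclude the Week 4 sample.

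A reader might infer three stronger things that the documents do not support:

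- **That the plan would yield a correlation of the wrong sign.** This follows only if values below LLOQ are set to LLOQ and decline is independent of baseline, and even then one setting gives 0.00. The plan states no substitution rule.
- **That every listed correlation is really with baseline load.** This is exact only among RVR4 achievers, with a constant substitute and a fixed 4-week divisor. Section 7.6 allows 7 days either side of Week 4. If actual visit dates are used and spread evenly over days 21 to 35 (an assumption), the correlation among achievers falls to about 0.72-0.74. Over all subjects, at 46% RVR4 with LLOQ 25, the measured slope correlates 0.60 with baseline and 0.61 with true decline. The documents give no expected RVR4 rate.
- **That all five items are circular.** SVR12, SVR24 and relapse rest on later samples. ETR shares a sample only if the end-of-treatment value is put into the slope.

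**Conclusion.** The point holds in limited form. The slope-RVR4 correlation is uninterpretable as a measure of prediction. That conclusion rests only on the sampling schedule and the definition of RVR4. For ETR, SVR12, SVR24 and relapse the weakness is censoring: how much the slope still says about true decline depends on an RVR4 rate that the documents do not give. The range of -0.27 to +0.73 shows how far the slope-RVR4 result can move with an unstated choice. It rests on assumed distributions and an assumed LLOQ of 15 or 25 IU/mL, and it is not a forecast for this trial. The point should be settled before analysis.

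**What to change.** In Section 3.3.2, delete the correlation of early kinetics with RVR4 and report RVR4 as a proportion. For ETR, SVR12, SVR24 and relapse, replace the slope by Week 4 status (below LLOQ, yes or no) cross-tabulated with each outcome. If a decline is still to be reported, define it as Day 0 to Week 4, treat values below LLOQ as left-censored rather than substituting a number, and show it beside baseline viral load. Put the same definitions in the statistical analysis plan.

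The change affects wording only and needs no added sampling. It costs one nominal secondary endpoint, and a yes/no Week 4 status carries coarser information than a measured decline.
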